10.0 WITHDRAWAL OF SUBJECTS

All potential participants will be thoroughly screened for eligibility after completing informed consent. The PI may withdraw subjects from participation at any time if the participant demonstrates or reports significant distress, is felt to be at risk of harm to themselves or to others, or is otherwise unable to complete the study protocol. Referrals to university and community resources will be made as indicated for all participants withdrawn from the study. The trial will be stopped under any of the following conditions: 1) there is clear evidence of harm; 2) there is no likelihood of the intervention demonstrating benefit, or 3) there is overwhelming evidence of the benefit of the intervention.

11.0 RISKS TO SUBJECTS

11.1 Overview

All medications have potential side effects. Ketamine has been well studied since its FDA approval in 1970. Based on extensive prior research with intravenous ketamine in the treatment of depression, the prevalence of the most commonly observed adverse reactions are estimated below by category. Participants will be informed of potential side effects associated with ketamine before study participation, and will be closely monitored both during the treatment and at each follow-up visit.

11.2 Physical Risks

The most significant physical adverse event from ketamine is a transient increase in blood pressure, which in previous studies was experienced by 29.8% of subjects with a mean systolic blood pressure increase of 19.6 mmHg +/- 12.8 mmHg and a mean diastolic blood pressure increase of 13.4 mmHg +/- 9.8 mmHg. Peak levels are reached on average 40 minutes post-treatment and resolve by 240 minutes post-treatment (Wan et al., 2015). Participants experiencing clinically significant hypertension (greater than 180 mmHg SBP or greater than 105 mmHg DBP, or greater than 30 mmHg SBP or DBP from baseline values) will be treated with standard of care hypertensives (e.g. clonidine) and monitored until symptom resolution.

The most prevalent physical adverse effect was transient sedation and occurs in approximately 16% of patients receiving ketamine. Sedation will be monitored via continuous clinical observation during interventional sessions. A medical emergency team will be called for participants that are unable to be

Page 17 of 22

aroused with painful trapezius squeeze or that experience hypoxia (i.e. a pulse oximeter reading of 92% or less), although in the investigative team's extensive experience using ketamine clinically for depression at these doses, such serious events have never occurred. Vital signs will be routinely monitored during treatment and emergency airway equipment will be immediately available. Subjects will be monitored post-dose by trained healthcare professionals (*e.g.* PI, co-I, or study nurse). Due to transient cognitive impairment associated with sedation, participants will not be allowed to drive themselves following the interventions. Subjects who do not have transportation and live within 20 miles will receive compensation for taxi, Uber or Lyft transportation to and from medication sessions up to \$100 each way. Subjects who live greater than 20 miles from the study site and cannot arrange their own transportation will be excluded from the study. Participants will be advised not to operate heavy machinery for at least 24 hours after the interventions.

There are also the standard risks associated with intramuscular injections including temporary local pain, irritation, or redness at the site of the injection. There is a very small (<1%) risk of infection, muscle fibrosis, or persistent muscle or nerve damage at the site of injection.

Other rare risks of ketamine include cystitis which are likely due to repeated use of ketamine. There is also a small risk of anaphylaxis.

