3.4 Schedule of Assessments

The instruments to be used are standardized, have good psychometric properties, and are widely used. The schedule of study assessments is provided in **Table 1**.

Page 8 of 22

Table 1: Schedule of Assessments

	Purpose	TIME POINT						
Instrument Name		BL	Tx 1-3	Follow-up				
		(Wk 0)	(Wk 1-3)	(Wk 4, 8)				
Self-Reports and Consents								
Informed Consent	Obtain informed consent	Х						
Demographics Form	Sample characterization	Х						
General Anxiety Disorder (GAD-7)	Self-report of anxiety symptom severity	х	х	Х				
Insomnia Severity Index (ISI)	Measure of insomnia severity	Х	Х	Х				
Mystical Experiences Questionnaire (MEQ)	Measure of perceptual experiences	Х	х	Х				
Five Facets of Mindfulness (FFMQ)	Assess aspects of mindfulness related	Х	Х	Х				
Fagerstrom Test of Nicotine Dependence (FTND)	Measure of nicotine dependence	х	х	Х				
Questionnaire on Smoking Urges (QSU)	Assessment of smoking cravings	х	х	Х				
Wisconsin Smoking Withdrawal Scale 2 (WSWS2)	Measures severity of smoking withdrawal	х	х	Х				
Timeline Follow- Back (TLFB)	Measure of substance use	Х	Х	Х				
Rhode Island Change Assessment (URICA)	Measure of stage of change	х	х	Х				
Beck Depression Inventory (BDI-II)	Self-report of depression symptom severity	X	×	X				
	Clinician Assess	ments						
History and Physical Exam	Eligibility assessment	Х						
Vital Signs Measurement	Obtain readings of blood pressure, pulse, temperature, respirations and pulse oximetry	Х	X*					
Pre-screening Questionnaire	To assess for basic eligibility criteria before completing a full baseline visit.	Х						

Page 9 of 22

Urine Pregnancy Test (female subjects only)	Eligibility assessment	х	Х	
Electrocardiogram (ECG; subjects with cardiac comorbidities or on QTc prolonging medications only)	Assessment of cardiac function	х		
Urine Drug Screen	Assess for use of psychoactive substances	Х		
Salivary cotinine level	Assessment of smoking status	Х	Х	Х

* Vital signs (blood pressure, pulse, respiratory rate, and pulse oximetry) will be obtained pre- and posttreatment. If there is an increase in systolic or diastolic blood pressure >30 mm Hg from baseline, or an increase in pulse rate >30 bpm from baseline, subjects will be treated with standard of care antihypertensive medications (i.e. clonidine) and the measurements will be repeated every 20 minutes until BP and pulse are within 30 points of the baseline values.

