3.6 Intervention Visit Procedures

Prior to administration of the study compounds, participants will complete self-report questionnaires and clinical assessments. Motivational enhancement therapy will be provided before and after ketamine administration, where the reduction of cigarettes and the subject's short and long term smoking-related goals will be discussed with the study physician. The study physician will then disinfect the subject's shoulder using an alcohol wipe, and the study physician will then administer the medication by intramuscular administration into the participant's deltoid muscle. Only individuals who are properly licensed will perform the injection of ketamine. Vital signs will be monitored prior to treatment and posttreatment. If during the post-administration observation period, ketamine administration causes an increase in systolic or diastolic blood pressure >30 mm Hg from baseline, or an increase in pulse rate >30 bpm from baseline, the subject will be treated with a standard of care antihypertensive (i.e. clonidine), and repeat vital sign measurements will be taken approximately every 20 minutes until blood pressure and pulse are within 30 points of baseline values. Medications will be stored in a DHEC compliant locked box within a locked room accessible only to study team members. If the subject experiences symptoms of hypertensive emergency, the subject will be treated with standard of care antihypertensive agents and referred for further assessment and treatment. Subjects experiencing serious adverse effects related to study participation will not receive further administration of ketamine and will be withdrawn from the study. After completion of the injection, when participants return to their neurocognitive baseline per clinical

assessment, they will complete assessments of their perceptual experience of the intervention. We will evaluate the effects of the 3 weekly interventions in 2 follow up sessions. Participants will return for followup assessments 4 and 8 weeks following final medication session. Follow-up visits may be conducted by telehealth. If the follow up is done via telehealth, participants will be given their saliva cotinine tests in advance either at an in person visit or by mail and asked to return them by mail.

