5.2 Inclusion Criteria

A subject may be eligible for enrollment if all the following inclusion criteria apply within the thirty days prior to first experimental session:

- 1. 21 to 65 years old.
- 2. Able to provide informed consent.
- 3. Be a daily cigarette smoker with multiple unsuccessful previous quit attempts, and report a continued desire to quit smoking.
- 4. Agree to abstain from smoking for the ketamine session from 1 hour before ketamine administration
- 5. Agree to refrain from using any psychoactive drugs, including alcoholic beverages, within 24 hours of ketamine administration. Exceptions include caffeine and nicotine.
- 6. Subjects taking other psychotropic medications must be maintained on a stable dose for at least four weeks before study initiation.
- 7. Be healthy as determined by screening for medical problems via a personal interview, a medical questionnaire, a physical examination, an electrocardiogram (ECG) to verify normal QTc intervals.
- Subjects with normal blood pressure not on antihypertensive medications or medication controlled hypertension as defined baseline visit systolic blood pressure (SBP) <140 mmHg or a diastolic blood pressure (DBP) <90 mmHg.

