5.3 Exclusion Criteria

Subjects will be excluded from the study if any of the following criteria apply:

- 1. Women who are pregnant (positive pregnancy test) or nursing, or are not practicing an effective means of birth control which can include oral, implant, intrauterine device, or patch contraceptive methods as well as barrier contraceptive methods, history of surgery such as hysterectomy or tubal ligation, or abstinence
- 2. Subjects who meet DSM-5 criteria for current or history of psychotic spectrum disorders or current depression or bipolar disorder based on clinical interview.
- 3. Subjects meeting DSM-5 criteria for current substance use disorder other than tobacco use disorder.
- 4. Subjects with hypertension as defined by a baseline visit systolic blood pressure (SBP) >140 mmHg or a diastolic blood pressure (DBP) >90 mmHg.
- 5. A history of allergic or other adverse reaction to ketamine (or its excipients).
- 6. Clinically significant physical exam findings or self-reported medical conditions for which a transient increase in blood pressure could be significantly detrimental (e.g. glaucoma, aneurysmal disease, cardiovascular disease, or end-stage renal disease).
- 7. Cardiovascular conditions: uncontrolled hypertension, angina, a clinically significant ECG abnormality (e.g., atrial fibrillation), TIA in the last 6 months, stroke, peripheral or pulmonary vascular disease
- 8. Subjects who live greater than 20 miles from the study site and cannot arrange their own transportation will be excluded from the study.
- 9. Subjects with clinically significant kidney or liver impairment.
- 10. Have any current neurological illnesses including, but not limited to, seizure disorders, frequent migraines or on prophylaxis, multiple sclerosis, movement disorders, history of significant head trauma, or CNS tumor.
- 11. Morbidly obese (BMI >40), or severely underweight as determined by medical examination.

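### Section 11.2 treats a diastolic pressure above 105 mmHg, but the visit procedure in 3.6 and the Table 1 footnote act only on the rise from baseline

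*Combined protocol and SAP*

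**What the plan says.** Section 11.2 (Physical Risks) describes clinically significant hypertension as "greater than 180 mmHg SBP or greater than 105 mmHg DBP, or greater than 30 mmHg SBP or DBP from baseline values". Such participants are to be treated and then followed until their symptoms resolve.

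Section 3.6 (Intervention Visit Procedures) gives the dosing-day rule. Treatment follows an "increase in systolic or diastolic blood pressure >30 mm Hg from baseline, or an increase in pulse rate >30 bpm from baseline", after which "repeat vital sign measurements will be taken approximately every 20 minutes until blood pressure and pulse are within 30 points of baseline values". The same section separately provides treatment for symptoms of hypertensive emergency, with no numeric limit.

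The footnote to Table 1 (section 3.4) uses the same relative triggers as 3.6 and the same end point: "the measurements will be repeated every 20 minutes until BP and pulse are within 30 points of the baseline values".

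Entry limits on blood pressure apply at the baseline visit. Section 5.2 admits participants with "baseline visit systolic blood pressure (SBP) <140 mmHg or a diastolic blood pressure (DBP) <90 mmHg", and section 5.3 excludes those with "baseline visit systolic blood pressure (SBP) >140 mmHg or a diastolic blood pressure (DBP) >90 mmHg".

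Vital signs are measured at the baseline visit and again around each dose: in the footnote they "will be obtained pre- and posttreatment", and in 3.6 "Vital signs will be monitored prior to treatment and posttreatment". Neither place says which of these measurements is the baseline for the 30-point rule.

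**The concern.** The plan states its dosing-day blood-pressure rule three times, and the statements differ. The one with absolute limits is in the risk section. The two that describe what happens at a visit have none. A participant who starts with a DBP in the upper part of the permitted range can pass 105 mmHg without a rise of more than 30.

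This matters because 11.2 names a transient rise in blood pressure as the most significant physical adverse event of ketamine, and safety and tolerability form part of Specific Aim 2. The rule applies at up to three dosing sessions per participant, or about 8 × 3 = 24 sessions. Someone working from 3.6 or Table 1 without 11.2 would find no prompt to treat a reading that 11.2 calls clinically significant, and no absolute level to reach before repeat readings stop.

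**Working it through.** The plan derives no figure on this point, so there is nothing to reproduce. The check compares the rules and then works through the thresholds.

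**1. The rules side by side**

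| | 11.2 | 3.6 and Table 1 footnote |
|---|---|---|
| Absolute trigger | SBP >180 or DBP >105 | none |
| Relative trigger | SBP or DBP rise >30 mmHg | SBP or DBP rise >30 mmHg, or pulse rise >30 bpm |
| End point | symptoms resolved | BP and pulse within 30 of baseline |

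**2. Where the DBP rules part.** With baseline DBP b, 11.2 acts above 105 and 3.6 acts above b + 30. A gap exists when b + 30 > 105, that is, b > 75. Its width is b + 30 − 105.

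- b = 75: 3.6 acts above 105. No gap.
- b = 76: 3.6 acts above 106. Gap 1 mmHg.
- b = 80: 3.6 acts above 110. Gap 5 mmHg.
- b = 85: 3.6 acts above 115. Gap 10 mmHg.
- b = 90: 3.6 acts above 120. Gap 15 mmHg.

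A DBP of exactly 90 is not excluded by 5.3 and can pass 5.2 through its *or*, so on the baseline-visit reading the affected range is 76 to 90. If baseline means the pre-dose value, no ceiling is stated and the range has no upper end.

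Example: 85 to 110 is a rise of 25. Under 11.2 it is treated. Under 3.6 it triggers nothing and is already within 30 of baseline. If there are no symptoms, the end point in 11.2 cannot be applied.

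**3. SBP.** From a baseline-visit SBP of 140 or less, a reading above 180 needs a rise of more than 40, which the relative rule already catches. A reading above 180 with a rise of 30 or less needs a starting SBP above 150, which is possible only if baseline means the pre-dose value.

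**4. Illustrative size.** Inputs from 11.2: DBP rise 13.4 ± 9.8, SBP rise 19.6 ± 12.8, experienced by 29.8% of subjects. Assumptions: ± is an SD, rises are normal, intravenous depression data carry over, and sessions treated because of pulse are not subtracted.

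- P(DBP rise >30): z = (30 − 13.4)/9.8 = 1.694, tail 0.045.
- P(SBP rise >30): z = (30 − 19.6)/12.8 = 0.8125, tail 0.208.
- DBP gap alone = P(105 − b < DBP rise ≤ 30).
- A session also triggers 3.6 if SBP rises by more than 30. With independent rises, multiply the DBP gap by 1 − 0.208 = 0.792. With perfectly correlated rises, take P(lower z < Z ≤ 0.8125).

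| b | lower z | DBP gap alone | independent | perfectly correlated |
|---|---|---|---|---|
| 76 | 1.592 | 0.011 | 0.008 | 0 |
| 80 | 1.184 | 0.073 | 0.058 | 0 |
| 85 | 0.673 | 0.205 | 0.162 | 0.042 |
| 90 | 0.163 | 0.390 | 0.309 | 0.227 |

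These apply if the means describe all subjects. If they describe only the 29.8% with a rise, multiply by 0.298, taking that share as the chance of a rise in a session. Independent: 0.003, 0.017, 0.048, 0.092. Perfectly correlated: 0, 0, 0.013, 0.068.

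**The case against.** The strongest reply is that this is an omission and not a contradiction. Section 11.2 is operative text in the same protocol and says these participants will be treated. Neither 3.6 nor Table 1 says that treatment is given *only* for a rise above 30. Treating when either condition is met satisfies every section. Nothing says that staff work from 3.6 alone, and a physician gives the injection at a small single-site study. Section 9.0 requires continuous medical monitoring until return to medical baseline, and 3.6 covers symptomatic hypertensive emergency.

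Most of this stands. It does not settle the end point. Even with the sections combined, an asymptomatic participant at 110 from 85 has already met the numeric criterion in 3.6, and the symptom criterion in 11.2 has nothing to act on. Section 9.0 keeps that participant observed but supplies neither a treatment trigger nor a number.

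It is also fair that the probabilities are weak evidence. On the reading that the means describe only those with a rise, even if every participant started at 80 the expected count is at most about 0.4 of 24 sessions (0.017 × 24), and at 85 about 1.2 (0.048 × 24). On the all-subjects reading the corresponding upper figures are 1.4 (0.058 × 24) and 3.9 (0.162 × 24). The baseline DBP distribution is not given, so none of these is a forecast.

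Three stronger readings are tempting, and the documents do not support them:

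- *Staff have no instruction to treat.* That is true only for someone using 3.6 or Table 1 without 11.2.
- *The procedure has no numeric end to monitoring.* It has one, relative to baseline. It lacks an absolute limit.
- *The missing SBP limit is an equal gap.* On the baseline-visit reading that limit is redundant.

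**Conclusion.** The point holds as a cross-section inconsistency worth correcting. For a baseline-visit DBP of 76 to 90, or higher if baseline is the pre-dose value, an asymptomatic reading above 105 with no rise over 30 is treated under 11.2 but not prompted by 3.6 or Table 1, and no stated end point serves it well. What remains is an inconsistent trigger and the lack of an absolute limit for ending repeat readings.

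The textual finding rests on no assumption beyond the entry limits. The illustrative chance per session spans 0% to 6% at a baseline of 80 and 1% to 16% at 85, across both readings of the means and from perfectly correlated to independent rises. It shows that the case is not far-fetched, and no more. A reader might infer that participants would be left unobserved or that the trial's results are compromised. Section 9.0 rules out the first, and the rule does not change how the feasibility outcome is defined or counted.

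**What to change.** Put one rule in 3.6 and the Table 1 footnote:

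- Treat if SBP is above 180 or DBP above 105 mmHg, or if SBP or DBP has risen by more than 30 mmHg, or pulse by more than 30 bpm.
- Repeat readings about every 20 minutes until BP and pulse are within 30 of baseline **and** BP is no longer above 180 systolic or 105 diastolic.
- State whether baseline is the baseline-visit value or the same-day pre-dose value. Both are already measured.
- Have 11.2 refer to this rule in place of its symptom-based end point.

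The SBP limit is included so that the sections match.

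The cost is a wording amendment in three places, with no new type of measurement. The downside is a few more treated or longer-observed sessions, with some extra repeat readings.

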11.3 Psychological Risks

Ketamine commonly causes transient dissociation (including derealization and depersonalization) and perceptual changes (e.g. distortion of time and space, sense of illusions). Based on prior studies these effects occur in 42% of subjects receiving ketamine. Anxiety occurs in 15% of subjects receiving ketamine. Psychological distress will be minimized with pre-treatment relaxation exercises and psychological reassurance as needed. In prior trials with ketamine for depression, these measures are sufficient to manage dissociation and anxiety in the overwhelming majority of participants. However, standard of care medications for agitation (e.g. benzodiazepines) will be available in the event that participants develop severe anxiety psychological distress unmitigated by reassurance and relaxation exercises. Psychiatric hospitalization will be arranged if needed, in the unlikely event of severe or prolonged psychiatric symptoms (e.g. lasting greater than four hours or the business day). Participants may also have emotional distress from answering the questionnaires, although this is mild in the investigators' experience with these instruments.

11.4 Abuse Liability

Ketamine is a psychoactive substance and is considered to have abuse liability. Ketamine is classified as Schedule III controlled substances (CIII). While there have been no randomized controlled trials evaluating the risk of subsequent illicit or recreational use of ketamine following medical administration (either for induction of sedation in conjunction with general anesthesia or in monitored off-label use for depression or pain management), in the extensive sub-anesthetic trials of ketamine for depression, there have been no published reports of illicit use developing after initial medical treatment with ketamine. None of the previous studies using ketamine in the treatment of substance use disorders reported illicit ketamine use following the ketamine interventions (Jones et al., 2018). Animal models using intracranial self-stimulation have demonstrated that ketamine fails to progress to self-administration, also suggesting a lack of abuse liability. Globally, the World Health Organization (WHO) evaluates the overall risks and abuse liability of ketamine; in their most recent report, the WHO affirmed that ketamine does not pose a global health risk, and again recommended its continued use (WHO, 2016). Substance use will be assessed at each visit throughout the study, and participants will be referred for ongoing care if they develop new or worsening substance use. If participants report illicit use of ketamine between intervention sessions, they will be withdrawn and referred for substance abuse treatment.

11.5 Social Risks: Adverse social consequences may arise if the participants' medical history or psychiatric history (including substance use history as well as psychiatric comorbidities) are inadvertently communicated to others.

11.6 Legal Risks: Legal risks may arise if individuals are homicidal or suicidal and make these intentions known to the PI project staff, who may then be required to notify authorities and the target of homicidal intent. There is also a legal and physical risk if participants were to drive or operate heavy machinery while cognitively impaired. Subject will be advised against operating heavy machinery following treatment.

11.7 Economic Risks: Subjects will be reimbursed for travel expenses including taxi, Uber or Lyft fare within 20 miles of study site as well as for any medical care related to study-related injuries.

11.8 Other Risks: While every possible effort will be made to protect the privacy of study participants, there is a risk of loss of confidentiality. There may also be unknown risks associated with the study procedure or intervention.

